The types of measures used to assess pain relief will include single rating scales; VAS, and multiple-dimension composite measures; Oswestry Low Back Pain Disability Questionnaire (ODI), The European Organisation for Research and Treatment of Cancer (EORTC) QLQ-C30 and QLQ-BM22.

VAS; is commonly used to rate various subjective experiences a VAS is usually a horizontal line, 100 mm in length, anchored by word descriptors at each end such as "no pain" on the left and "severe pain" on the right, as illustrated in Fig. 1. The patient marks on the line three pain ratings, corresponding to current, best and worst intensity of pain experienced over the past 24 hours. The average of the 3 ratings will be used to represent the patient's level of pain over the previous 24 hours.. The VAS score is determined by measuring in millimeters from the left hand end of the line to the point that the patient marks.

[figure not shown]

Fig.(1) VAS, used in patients diary for guide in self-score pain.

The VAS has consistently demonstrated sensitivity to changes in cancer pain associated with treatment or time) and usually shows strong associations with other pain intensity ratings, it appears adequately valid and reliable as measures of pain intensity among the many different samples of persons with cancer ¹⁷.

ODI is a self-administered questionnaire divided into ten sections, each with six items designed to assess limitations of various activities of daily living. Each section is scored on a 0 to 5 scale, with 5 representing the greatest disability. The index is calculated by dividing

the summed score by the total possible score, which is then multiplied by 100 and expressed as a percentage. Thus, for every question not answered, the denominator is reduced by 5. If a patient marked more than one statement for a question, the highest scoring statement is recorded as the true indication of disability. It takes 3.5 to 5 minutes to complete the questionnaire and approximately 1 minute to score. The scores are assessed from 0% to 20% to indicate minimal disability, 20% to 40%, to indicate moderate disability, 40% to 60% to indicate severe disability, 60% to 80% to indicate crippled, and 80% to 100% to indicate bed bound or exaggerating their symptoms¹⁸. The ODI is the most commonly used disease specific patient reported outcome tool to measure functional disability related to back pain¹⁹.

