QOL. The EORTC **QLQ-BM22** is a sub-module of the QLQ-C30 and is an internationally recognized and validated scale used to measure QOL in bone metastases patients ²³. The QLQ-BM22, includes four subscales: painful sites, pain characteristics, functional interference, and psychosocial aspects. Both questionnaires use a 4-point Likert scale ranging from 1 (not at all) to 4 (very much) to rate each item, except for the final 2 question of the QLQ-C30 pertaining to overall QOL which is scored from 1 (very poor) to 7 (excellent). Each subscale is then linearly converted to a score from 0 to 100. For the QLQ-BM22, a higher score indicates worse symptom burden for painful sites and pain characteristics, and better functioning for functional interference and psychosocial aspects. For the QLQ-30, higher scores in the emotional, physical, and QOL scales indicate greater functioning and better ²¹.

VAS, ODI, QLQ-C30 and QLQ-BM22 will be used to evaluate pain, quality of life, and performance status before the procedure and at 3 days and 1, 3, 6 months after the procedure²⁴.

In the holding area, midazolam 0.02 mg/kg IV will be given after fixation of a 20 G cannula. All RF procedures will be performed in the hospital outpatient ambulatory care setting using local anesthesia and conscious sedation as necessary, with fluoroscopic guidance to facilitate needle placement. The segmental spinal levels treated will be selected based on the patients' pain referral pattern as determined by history and physical examination findings. After sterile skin preparation, RF will be performed with the patient in the prone position with mild flexion of the spine and the fluoroscopy beam positioned in an antero-posterior (AP) direction. A 10 cm RF needle 20 G with a 10 mm active tip. The image intensifier will be rotated in a cephalo-caudad direction until the endplates of the adjacent thoracic intervertebral discs is lined up and the transverse processes became discernable from the ribs. The needle is then inserted in a slightly medial-cephalad direction under the transverse processes, and using lateral fluoroscopic imaging, incrementally walking into the thoracic intervertebral foramen . The correct position of the needle's tip should be exactly in line with the facet joint spaces on the anteroposterior projection of the image intensifier, and in the posterior part of the foramen on the lateral projection. Once correct needle position is

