According to studies ^(13,15,16) , to see a significant reduction in VAS defined as at least 50% reduction, ODI, QLQ-C30 and QLQ-BM22 score ($P < 0.01$) with a background standard deviation of 1.0, significance level of 0.05 and power of a test of 80%, minimum number of patients needed would be 25 per group. Because difference in VAS , ODI, QLQ-C30 and QLQ-BM22 score will be more evidenced with control group, the number needed would be much smaller , so the total number needed in the present study would be 69 patients that will be randomized into 3 equal groups. For non-parametric correction, we increased the number to 27 patients for each group.

2- Statistical analysis plan:

Data will be analyzed using SPSS version 18.0. Numerical data will be presented as mean, standard deviation or median and range as appropriate. Categorical data will be presented as numbers and proportions. Mixed models ANOVA will be used to show effect of time on pain score and also to evaluate group interaction. Non-parametric tests ; Friedman's test will be used if data did not show normal distribution. Significance level will be considered at 0.05.

REFERENCES

1. **Smith HS.** and **Barkin RL**, Painful boney metastases, American Journal of Therapeutics , 2014 ;21(2):106-130.
2. **Patrick W.**, Bone Cancer Pain: From Mechanism to Therapy, Current opinion in supportive and palliative care 2014 ; 8(2): 83–90.
4. **Bhatia A.** , Questions Regarding "Pulsed Radiofrequency for Chronic Intractable Lumbosacral Radicular Pain: A Six-Month Cohort Study", Pain Medicine 2016; 17(5):989.
6. **R. Carter W. Jones III**, Neuroinflammatory effects of Radiofrequency, European Journal of Pain 2014; 18 :149-150.
7. **Zeldin A. and Ioscovich A.**, Pulsed Radiofrequency for Metastatic Pain Treatment, Pain Physician 2008; 11:921-922 .

8. **Young-Chang P. Arai, Makoto N., Yoshihiro Y., Maki A., Miki K., Chiharu S., Akiko K., Kazuyo K., and Tatsunori I.,** Dorsal Root Ganglion Pulsed Radiofrequency for the Management of Intractable Vertebral Metastatic Pain: A Case Series, *Pain Medicine* 2015; 16:1007 – 1012.

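### The 80% power claim rests on one unitless SD of 1.0 for four differently scaled primary outcomes; it is unsupported for ODI, QLQ-C30 and QLQ-BM22, and not reproducible for VAS

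*Combined protocol and SAP*

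**What the plan says.** The sample-size paragraph (STATISTICS, 1 - Sample size estimation) sets the aim for all four instruments in one clause: "to see a significant reduction in VAS defined as at least 50% reduction, ODI, QLQ-C30 and QLQ-BM22 score". The planning inputs follow once, for all of them: "with a background standard deviation of 1.0, significance level of 0.05 and power of a test of 80" per cent. The result is "minimum number of patients needed would be 25 per group". The paragraph then argues that fewer patients are needed because differences from control will be larger, so that "the total number needed in the present study would be 69 patients" (23 per group). It finally raises the number to 27 per group as a non-parametric correction.

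OUTCOME AND ASSESSMENT lists all four instruments as primary, at 1, 3 and 6 months. PATIENTS AND METHODS gives the scoring:

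- **ODI:** ten sections scored 0 to 5; the index divides "the summed score by the total possible score, which is then multiplied by 100 and expressed as a percentage".
- **QLQ-C30 and QLQ-BM22:** items are rated 1 to 4, except the two overall QOL items, rated 1 to 7. "Each subscale is then linearly converted to a score from 0 to 100".
- **VAS:** read in millimetres on a 100 mm line, whereas the second inclusion criterion requires a VAS above 5.

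No other SD appears in the document. The only target difference, a reduction of at least 50%, is attached to VAS.

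**The concern.** An SD has the unit of its scale. A single value of 1.0 cannot be assumed to describe four instruments with different scoring, and on a percentage or 0-100 scale it would mean that nearly all patients have the same score. Power depends on the ratio of the difference to the SD. For three of the four primary outcomes the plan gives no difference and an SD that does not fit; for the fourth, the unit is unclear.

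The risk lies in interpretation. As written, the plan lets a reader take a null result on ODI or quality of life as coming from a comparison with 80% power, when moderate differences could have been missed.

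**Working it through.** **Inputs from the plan.** SD 1.0, alpha 0.05 (sidedness not stated; two-sided taken here), power 80%, and 25, then 23, then 27 per group. I treat each calculation as one pairwise comparison of means with no dropout, since the plan makes no dropout allowance.

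**1. Reproducing 25 per group.** By the normal approximation, n per group = 2 × (1.960 + 0.842)² / d² = 2 × 7.849 / d², where d is the difference divided by the SD.

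- d = 0.8: 15.70 / 0.64 = 24.5, rounded up to 25. This matches, but 0.8 is not stated anywhere. The t-test version gives 25.5, so 26.
- Halving a VAS of 5, taken as the between-group difference: d = 2.5 / 1.0 = 2.5, so 15.70 / 6.25 = 2.5, i.e. 3 per group. At so small a number the t-test is the better guide: power is 64% with 3 per group and 84% with 4, so about 4. This does not match 25, and a higher starting score would need still fewer.
- The same sentence also carries P < 0.01. A difference of 1.0 SD at two-sided 0.01 gives 24 (t-test 26). So 25 does not identify a unique set of inputs.

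**2. What an SD of 1.0 would mean in scale points.**

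- ODI step: 100 / (10 × 5) = 2 points. An SD of 1.0 arises if patients split evenly between two adjacent scores (2 × √(0.5 × 0.5) = 1.0), or if 75% share one score and 12.5% sit on each neighbour (variance 0.25 × 2² = 1). By contrast, scores spread evenly over just one of the protocol's 20-point disability bands have an SD of 20 / √12 = 5.8 (6.3 on the 2-point grid).
- Overall QOL (two items, each 1 to 7): step 100 / 12 = 8.3 points. If only two adjacent scores occur, SD 1.0 requires p(1 − p) = 1 / 8.33² = 0.0144, so p = 0.015: about 98.5% of patients on the same score.
- A single 1-to-4 item: step 100 / 3 = 33.3 points. One patient in 25 who differs by one step already gives an SD of 33.3 × √(0.04 × 0.96) = 6.5.

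The protocol does not list the number of items in most QLQ subscales, so I give steps only where they follow from its text or from a single item.

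**3. What 27 per arm can detect.** The two-sided 0.05 t-test with 27 per arm has 80% power at d = 0.777. The document gives no SD for the 0-100 scales; the SDs and the differences below are assumptions.

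| Assumed SD | Detectable difference (0.777 × SD) | Power, 10 points | Power, 25 points |
|---|---|---|---|
| 15 | 11.7 | 67% | over 99% |
| 20 | 15.5 | 44% | over 99% |
| 25 | 19.4 | 30% | 95% |
| 30 | 23.3 | 23% | 85% |

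Taken literally, SD 1.0 would give a detectable difference of 0.78 points, which is less than one ODI step.

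**The case against.** The strongest defence is that SD 1.0 is a standardised unit and the trial was sized for a difference of 0.8 SD. That reproduces 25 exactly by the normal approximation, and at d = 0.8 the final 27 per arm has 82% power (t-test) on any scale. The arithmetic stands, and this may well be how the number was obtained. But the plan does not say so: it calls the figure a background SD, appeals to cited studies, and states no standardised effect. Even on this reading, the reader needs each scale's SD to know what difference 0.8 SD represents.

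Three stronger readings are tempting, and the documents do not support them:

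- *That 80% power is false for ODI and the QLQ scales.* With no target difference stated, it cannot be shown false. A 25-point difference, for instance a halving from an assumed score of 50, keeps 85% power even at SD 30.
- *That SD 1.0 is impossible on ODI.* The two distributions in the working have exactly that SD. The argument is implausibility, not contradiction.
- *That the defect spares VAS, so the power claim could simply be restricted to it.* The VAS unit is itself inconsistent, and the stated 50% reduction does not lead to 25.

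It can also be said that recruitment ended on 30 July 2018 and the document is dated 31 March 2019, so rewording cannot alter the design. That is true, and nothing in the plan prescribes how a null result is to be read. It limits the point to how the power is described and how results are reported.

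**Conclusion.** The point holds in this form: the 80% power is unsupported for ODI, QLQ-C30 and QLQ-BM22, because an SD of 1.0 scale point is not credible on these scales and no difference is given; the VAS calculation cannot be reproduced from its stated inputs. What the design does offer is 80% power for a standardised difference of about 0.78, for one pairwise comparison at two-sided 0.05 with all 27 patients per arm analysed. Whether that is adequate depends on the SD and on the difference that matters. Over assumed SDs of 15 to 25, power runs from 30% to 67% for 10 points and is at least 95% for 25 points. It would be wrong to infer that the trial is underpowered on these outcomes; the documents do not settle that either way.

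**What to change.** In the sample-size paragraph:

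1. Remove SD 1.0 as a common SD for the four instruments.
2. Restate the calculation: 27 per arm gives 80% power for a standardised difference of about 0.78 (two-sided 0.05 t-test, one pairwise comparison, no dropout).
3. For each primary scale, give the assumed SD with its source and the resulting detectable difference, 0.78 × SD. Include VAS, state its unit, and reconcile the millimetre scoring with the inclusion criterion.

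In reporting, give null results on these scales with confidence intervals, and do not present them as findings from a comparison with 80% power.

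The cost is one reworded paragraph and a stated power that becomes conditional and less favourable. No extra patients are needed.

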This is a Prospective Randomized Controlled trial that will be conducted at the National Cancer Institute. All patients who are eligible for the study will be included and randomized into 3 equal groups.

PATIENTS AND METHODS

After approval from the Ethics Committee at the National Cancer Institute, Cairo University, and obtaining written informed consent, eighty-one patients with thoracic segmental pain due to metastasis, unresponsive to conventional therapy and meeting the inclusion criteria will be randomly assigned to either one of the two types of treatment, PRF or TRF lesioning of the DRG or the control group. Patients will be carefully evaluated for neurologic deficits and side effects. Assessment of pain will be done at baseline then at 1, 3, 6 months after the procedure. Randomization will be done using randomized permuted block design. Randomization list will be generated through random.org online site.

INCLUSION CRITERIA:

1. A greater than 6-month history of segmental pain of thoracic vertebral body metastasis origin.

2. Unsatisfactory pain control with oral pharmacotherapy including strong opioid with VAS >5 .
3. Absence of a chronic or progressive motor deficit.
4. Absence of significant sensory deficit.
5. No indication for percutaneous or open surgical intervention.
6. Magnetic resonance imaging and Computed Tomography evidence of thoracic involvement.
7. ASA status of II to III .
8. Age \geq 18 .
9. Body mass index (BMI) :less than forty and more than twenty .
10. Informed consent

EXCLUSION CRITERIA:

1. Known sensitivity or contraindication to injected materials: local anesthetics.
2. History of psychological disorders.
3. Evidence of significant neurological deficit.
4. Inability to lie prone.
5. Local contraindication to procedure e.g. local sepsis at the site of intervention, coagulopathy.
6. Patient refusal.

Patients will be randomly assigned and divided into 3 equal comparable groups. Before the procedure, laboratory investigations, Dorsal X-ray, CT and MRI will be done. All Patients will be interviewed and examined by physicians trained in interventional pain management. Patients will be carefully assessed on physical exam for sensory, motor, or reflex deficit and

carefully documented. Patients will be informed about the technique of the blocks, and written informed consents will be obtained.

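### The sample size text goes below its own minimum of 25 per group for a reason that cannot apply to PRF versus TRF, and its stated inputs do not lead to 25 or to the planned 27

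*Combined protocol and SAP*

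**What the plan says.** The title names thermal versus pulsed radiofrequency as the comparison; a third, control group has needle placement and local anaesthetic without lesioning. The section on sample size estimation under STATISTICS proceeds in four steps.

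- Target: "to see a significant reduction in VAS defined as at least 50% reduction", together with ODI, QLQ-C30 and QLQ-BM22, for which no size of change is given.
- Inputs and first result: "with a background standard deviation of 1.0, significance level of 0.05 and power of a test of 80" per cent, from which the "minimum number of patients needed would be 25 per group".
- Reduction: "so the total number needed in the present study would be 69 patients that will be randomized into 3 equal groups". The reason given is that the differences "will be more evidenced with control group, the number needed would be much smaller".
- Increase: "For non-parametric correction, we increased the number to 27 patients for each group".

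PATIENTS AND METHODS agrees with the last step: it plans for "eighty-one patients with thoracic segmental pain due to metastasis", and 27 × 3 = 81. The analysis plan specifies mixed-model ANOVA and adds that "Friedman's test will be used if data did not show normal distribution". The primary outcome section lists all four instruments at 1, 3 and 6 months.

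**The concern.** A number presented as a minimum is undercut one sentence later. The reason given concerns comparisons with control only, yet the reduction is applied to all three arms, including the two whose head-to-head comparison gives the trial its title. The number then rises again by an unstated amount, so the reader cannot tell whether the final figure restores the minimum.

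The 80% power is also not attached to any difference between groups. A 50% reduction is a change from baseline. Without the corresponding change in the comparator it does not define a contrast between arms.

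What is at stake is interpretation. If PRF and TRF do not differ significantly on one of the four primary instruments, a reader may take the 80% as evidence that a relevant difference would have been found. The text does not say what difference that would be, on which scale, or between which arms.

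**Working it through.** **Inputs.** From the sample size section: SD 1.0 (no unit, one value for four instruments), significance level 0.05, power 80%, and per-group numbers of 25, then 69/3 = 23, then 27. From the inclusion criteria: VAS above 5. Sidedness is not stated; two-sided is assumed below.

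**Step 1: can 25 be reproduced from the stated inputs?** The usual formula is n per group = 2(1.960 + 0.842)² SD²/Δ². The plan gives no between-group Δ. The nearest literal reading takes half of a VAS of 5, so Δ = 2.5, with SD 1.0 and no change in control (an assumption). Then n = 2 × 7.85/6.25 = 2.5, or 3 per group. With the exact t distribution, 3 per group has 64% power and 4 per group has 84%. This reading therefore gives about 4, not 25.

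**Step 2: what would give 25?** It can only be solved backwards, and the answer is not unique.

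- Two-sided two-sample t-test at 0.05: 25 per group has 80% power for 0.81 SD. By the formula above, Δ = 0.8 gives 2 × 7.85/0.64 = 24.5, so 25.
- One-sided test at 0.05 (normal approximation): 0.70 SD.
- Three-group ANOVA: f = 0.37.
- Responder comparison with assumed rates: 50% versus 10% with continuity correction gives 25, and so does 90% versus 55% without it.

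The text states none of these.

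**Step 3: the cut to 23.** 25 × 3 = 75; 69/3 = 23. If the Δ behind 25 gives exactly 80% power by t-test (0.81 SD), 23 per group gives 76.5% and 27 gives 83.0% for that same Δ. A larger difference from control raises power for PRF versus control and TRF versus control. It leaves Δ for PRF versus TRF unchanged, so it cannot lower the n for that comparison.

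**Step 4: the rise to 27.** Three correction factors, all assumed, are applied to each possible base and rounded up:

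| Factor | From 23 | From 25 |
|---|---|---|
| × 1.15 | 26.45 → 27 | 28.75 → 29 |
| ÷ 0.864 | 26.62 → 27 | 28.94 → 29 |
| ÷ 0.955 | 24.08 → 25 | 26.18 → 27 |

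After rounding up, 27 is reached from 23 with a factor above 26/23 = 1.130 and up to 27/23 = 1.174. From 25 the factor must be above 26/25 = 1.04 and up to 27/25 = 1.08. Neither the factor nor its base can be identified. The only non-parametric test named, Friedman's, compares time points within patients, so it does not reveal which between-group test the correction was for.

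**Step 5: can SD 1.0 be a raw SD?** With all ten ODI sections answered, the score moves in steps of 100/(10 × 5) = 2 points. An SD of 1.0 would require, for example, all patients split evenly over two neighbouring scores (0.5 × 0.5 × 2² = 1). The QLQ-C30 overall quality-of-life scale has two items scored 1 to 7, rescaled to 0–100, so its step is 100/(2 × 6) = 8.33. On two neighbouring scores, p(1 − p) × 8.33² = 1 gives p = 0.0146, so about 98.5% of patients would share one score. Neither is credible as a raw SD on a 0–100 scale. On the VAS, 1.0 could be a raw SD on a 0–10 scale, but the assessment text measures the VAS in millimetres on a 100 mm line while the inclusion criterion uses a threshold of 5.

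**Step 6: what 27 per group supports.** For one unadjusted two-sided 5% pairwise comparison of a single continuous measure at one time point, 27 analysed per group has 80% power for 0.777, or about 0.78 SD (noncentral t, 52 degrees of freedom). The 95% CI half-width is t × √(2/n) = 2.007 × √(2/27) = 0.546, or about 0.55 SD. With 20 analysed per group (an assumption) these become 0.91 SD and 0.64 SD.

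**The case against.** The best defence is that the final number may be sound. At a rank-test efficiency of 0.955, the stated minimum of 25 becomes 25/0.955 = 26.18, rounded up to exactly 27, and the 69 step then has no effect on the planned size. That possibility stands. It is not established, because the opposite holds at 0.864 or with a 15% increase, and the plan says which base it used only by the order of its sentences.

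The difference behind 25 may also exist in calculation records or in the studies cited for the calculation. A reader might infer that no between-group difference was ever chosen. The documents show only that none is written down, so the request must be to state it or to say that it cannot be recovered.

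It is also fair to say that a t-test at one time point is not the planned analysis. With baseline adjustment at an assumed correlation of 0.5 to 0.7, 0.777 × √(1 − r²) gives 0.67 to 0.55 SD, so the planned mixed model may do better than 0.78 SD. A between-group rank test would do somewhat worse: 27 × 0.955 = 25.8 and 27 × 0.864 = 23.3 effective patients, or about 0.80 to 0.84 SD. The restated figure needs these qualifications.

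SD 1.0 may have been meant as a standardised unit. If so, the text does not say it, and the standardised difference is still missing. The VAS mismatch is probably a slip of notation and is minor.

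**Conclusion.** The sample size text is wrong as written. It sets 23 per group below its own minimum of 25, for a reason that cannot apply to PRF versus TRF. Its stated inputs lead to about 4 per group on the literal reading (2.5 points, SD 1.0, control unchanged: assumptions), not 25. The planned 27 cannot be traced to either base.

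A reader might infer that the trial is underpowered. The documents do not support that: 27 exceeds the stated minimum of 25, and 25 itself belongs to no stated difference. What is lost is the meaning of the 80%, which cannot be used to interpret a null PRF versus TRF result.

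The 0.78 SD and 0.55 SD figures assume 27 analysed per group, a two-sided 5% level, one pairwise comparison, one continuous measure, one time point and no adjustment. The documents give 81 as the planned number and do not report how many patients were enrolled or analysed.

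**What to change.** Keep 81 patients. In a dated correction, with the existing text left visible:

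1. Withdraw the step from 25 per group to 69 in total.
2. State the between-group difference, its scale and the comparison behind 25, and the correction factor behind 27 with the number it was applied to, or say that these cannot be recovered.
3. Restate the power along these lines:

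> With 27 analysed per group, one unadjusted two-sided 5% pairwise comparison of a single continuous measure at one time point has 80% power for about 0.78 SD (PRF–TRF 95% CI half-width about 0.55 SD). Fewer analysed patients or a rank test make this less favourable; baseline adjustment or repeated measures may make it more favourable. The 80% is not a claim about any raw difference in VAS, ODI, QLQ-C30 or QLQ-BM22.

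4. Interpret a null PRF versus TRF result from its confidence interval.
5. As a minor point, use one VAS unit in the inclusion criteria, the assessment section and the sample size section.

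The cost is wording only, with no change to patients, outcomes or analysis. The stated power claim becomes less favourable. Recruitment closed on 30 July 2018, so six-month follow-up would have ended about 30 January 2019, before the document date of 31 March 2019. The correction must therefore carry its own date, and the SD-unit figures must not be derived from observed data.

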Comparison between Dorsal Root Ganglion Thermal Radiofrequency versus Pulsed Radiofrequency for the Management of Intractable Metastatic Pain in Thoracic Vertebral Body

Trial registration on Clinical Trial.gov: Clinical Trials

NCT03204942 on the 2nd of July 2017

Protocol date approval by National Cancer Institute (NCI)

Anaesthesia and Pain Management Department: 11 September 2016

NCI Cairo Ethics Committee approval: 14th of February 2017

Recruitment started: 30 July 2017

Recruitment Completed: 30 July 2018

Document Date (the date on which the uploaded document was most recently updated): 31 March 2019

INTRODUCTION

Metastatic disease to the bone has been a crippling devastating complication of various cancers, with unbearable pain ¹. Knowledge surrounding the pathophysiology of painful osseous metastases is rapidly changing ². Metastatic bone pain is characteristic of cancer pain and is a form of refractory cancer pain, as the pain includes not only nociceptive but also neuropathic pain that induces a peripheral and central sensitization.

The development of medication dose-limiting side effects, limits analgesic efficacy in nearly 42% of cancer pain patients ³.

In recent years the use of pulsed radiofrequency (PRF) to treat chronic pain conditions has generated intense interest in the pain community ⁴. PRF is a minimally invasive, target-selective technique that has reported benefit at reducing post-amputation stump pain, chronic radicular/ganglion pain , neuropathic pain , and arthropathic pain ^{5,6}.

In **2008**, **Zeldin** and **Ioscovich** published 3 cases of patients who suffered from uncontrolled vertebral/paravertebral metastatic pain and were successfully treated by fluoroscopically

guided selective dorsal root ganglion (DRG) PRF (PMG-230 Baylis Medical com. Inc. Canada) ⁷. They concluded that that PRF on selective DRG bilaterally under fluoroscopic guidance in patients with pain secondary to metastasis in the Thoracic vertebral body and who were unsuccessfully treated with opioids, may offer new opportunities for metastatic pain treatment and encourage future studies.

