confirmed by image and since neural tissue cannot be seen on plain radiographs and the DRG may vary with respect to its spatial relationship with the intervertebral foramen, so the location of the needle tip will confirmed not only by image but also by sensory stimulation at 50 Hz. The point of maximum stimulation is where sensory response in the painful dermatome can be elicited with stimuli below 0.5 V intensity and this is designated to be the location of the DRG. Slight redirection can be done to optimize the stimulation; injection of contrast reveals epidural uptake. After establishing the site for the RF, 1 ml 2% lidocaine should be injected through the needle. The needle is then connected to a RF generator (Baylis Medical com. Inc. Canada).

Group 1: Patients will receive PRF with temperature 42°C for 480 sec., 2 active cycles per second of 20 milliseconds each , with a voltage output 40 to 60-V range, impedance ranges between 150 and 400 Ohms at all levels using Fluoroscopic guidance (FG). The block will be done as that described by **Young-Chang P. et al** ⁸.

Group 2: Patients will receive TRF with temperature 80°C for 90 sec., 2 cycles, using FG . The block will be done as that described by **Ken-ichiro U** ¹⁶.

Group 3: The control group having identical needle placement and preparation without the RF lesioning (only local anesthetic).

OUTCOME AND ASSESSMENT

Primary outcome measure:

It will include:-

-VAS, ODI, QLQ-C30 and QLQ-BM22 to evaluate pain, quality of life, and performance status at 1, 3, 6 months after the procedure.

Secondary outcome measures:

It will include :-

- Neurological defects .
- Dysthesia and hypoesthesia.
- Change in physical activities, and analgesic use.
- Any other complication from either the technique as pneumothorax or local anesthetic, anesthesia dolorosa and burning pain.
- Patients' satisfaction with analgesia through a phone call a week after procedure on 5-level likert scale, (not satisfied at all, only slightly satisfied, somewhat or partly satisfied, very satisfied, perfectly satisfied)

STATISTICS

1 - Sample size estimation:

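### Arms are compared only through an omnibus interaction, with no named pair and no baseline covariate, and the one named non-parametric fallback cannot compare arms

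*Combined protocol and SAP*

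**What the plan says.** The Statistics section (part 2, statistical analysis plan) gives the inferential plan in two sentences. The main analysis is: "Mixed models ANOVA will be used to show effect of time on pain score and also to evaluate group interaction". The fallback is: "Friedman's test will be used if data did not show normal distribution". Neither sentence names a pair of arms, a visit for the comparison or a covariate.

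The title poses a pairwise question: "Comparison between Dorsal Root Ganglion Thermal Radiofrequency versus Pulsed Radiofrequency for the Management of Intractable Metastatic Pain in Thoracic Vertebral Body". The trial randomises 81 patients, 27 to each of pulsed radiofrequency (PRF), thermal radiofrequency (TRF) and control.

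The visit lists differ between sections:

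- Patients and Methods, opening paragraph: "Assessment of pain will be done at baseline then at 1, 3, 6 months after the procedure".
- Patients and Methods, after the description of the scales: "performance status before the procedure and at 3 days and 1, 3, 6 months after the procedure".
- Primary outcome measure: "to evaluate pain, quality of life, and performance status at 1, 3, 6 months after the procedure".

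The first two lists include a baseline measurement. The second adds day 3. The third has neither.

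**The concern.** A three-arm interaction gives a single p-value. It does not say which arms differ, by how much or when, so the comparison in the title has no planned estimate or confidence interval.

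Baseline is already measured. Using it as a covariate would correct chance imbalance and, if it predicts follow-up, narrow the intervals. If it enters only as another time level, the interaction rests partly on change-from-baseline contrasts, which are less precise.

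The fallback matters more. If the data are judged non-normal, the analyst moves to a test that does not involve arm. The trial could then report a change over time and have no formal result on its randomised question.

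**Working it through.** **1. Friedman's test.** It ranks each patient's visits against each other and sums the ranks by visit. Arm does not enter the statistic: shuffle the arm labels and the result is the same. This needs no assumed number.

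**2. What the interaction tests.** This depends on which visit list is used.

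- With only months 1, 3 and 6, an arm difference that is constant over visits contributes nothing to the interaction, so its power equals the 5% test level. The group main effect would detect such a difference, but the plan does not name it.
- With baseline as a time level, the interaction includes change-from-baseline contrasts.

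**3. Inputs for precision.** From the documents: 27 per arm, N = 81, significance level 0.05 (taken as two-sided). Assumed, because the documents do not give them: correlation ρ = 0.3 / 0.5 / 0.7 between all visits, and equal variances. Results are in SD units.

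**4. Single-visit variances per patient.**

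- Follow-up only: 1.
- Change from baseline: 2(1 − ρ).
- Baseline-adjusted: 1 − ρ², times 1 + 1/76 = 1.013 for estimating the slope.

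Leaving out the slope cost, change over adjusted is 2(1 − ρ)/(1 − ρ²) = 2/(1 + ρ) = 1.54 / 1.33 / 1.18, which is 54 / 33 / 18% more variance.

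The 95% half-width for a pair of arms is t × √(2/27) × √variance, with t about 1.99 and √(2/27) = 0.272:

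| ρ | Adjusted | Change | Follow-up only |
|---|---|---|---|
| 0.3 | 0.52 | 0.64 | 0.54 |
| 0.5 | 0.47 | 0.54 | 0.54 |
| 0.7 | 0.39 | 0.42 | 0.54 |

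**5. Break-even against follow-up only.** (1 − ρ²)(1 + 1/76) = 1 gives ρ = √(1/77) = 0.114. With 20 per arm analysed (N = 60) it is √(1/56) = 0.134. At ρ = 0 the cost of adjusting is 1/76, about 1.3% in variance.

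**6. Effect of the entry rule.** Patients must have "Unsatisfactory pain control with oral pharmacotherapy including strong opioid with VAS >5", which may narrow the baseline range. Suppose it halves the baseline variance (assumed).

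- The excess variance of change scores becomes 0.5(1 − ρ)/(1 + ρ) = 27 / 17 / 9%.
- The reduction against follow-up only becomes 0.5ρ²/(1 − 0.5ρ²) = 5 / 14 / 32%, compared with ρ² = 9 / 25 / 49% without narrowing. Both are before the 1.3% cost.

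**7. Adjusted mean of months 1, 3 and 6 against the interaction.** The documents state no between-arm difference, so effects against control of 0.81 and 0.40 SD at month 1 are assumed. The 0.81 is what 25 per group, SD 1.0 and 80% power detect by t test; the 0.40 has no source. Both tests are three-arm F tests. The adjusted mean has variance (1 + 2ρ)/3 − ρ², and the interaction has error variance 1 − ρ.

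| Assumed time course | Adjusted mean, power at ρ = 0.3 / 0.5 / 0.7 | Interaction, power at ρ = 0.3 / 0.5 / 0.7 |
|---|---|---|
| Sustained; baseline and 3 visits | 98 / 99 / >99% | 60 / 78 / 96% |
| Fades to zero at month 6; day 3 included, effect as at month 1 | 54 / 56 / 70% | 70 / 87 / 99% |

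With day 3 included and a fade from 0.81 to 0.30 SD at month 6, the interaction is also slightly ahead at ρ = 0.7 (94% v 92%). Neither test is better for every time course.

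**The case against.** The strongest reply is that the planned mixed ANOVA is a valid analysis and that covariate adjustment is an efficiency choice. That stands for the parametric route. Several stronger readings are tempting, and the documents do not support them:

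- **That the plan has no between-arm test.** It has one: the group interaction compares arms. What is missing is a named pairwise contrast with an estimate.
- **That baseline adjustment always wins.** The 0.11 threshold applies to an unadjusted single-visit contrast with all 81 patients analysed, and it rises with attrition. At ρ = 0.3 the gain there is 0.52 v 0.54 SD. A three-visit average can also lose to the planned interaction when effects fade.
- **That the trial is underpowered for PRF against TRF.** The documents give no difference between those arms, so any such power figure only reflects the effect that the reader assumes.
- **That the fallback would produce false claims about arms.** If Friedman's test were run arm by arm, with three identical arms each falling by an assumed 0.5 SD, some but not all arms would be significant in about 75 / 71 / 41% of simulated trials. But the plan does not propose inferring arm differences that way, and detecting a real fall over time is correct. The supported point is only that the named test does not compare arms.

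The plan does refer to non-parametric tests in the plural, so another test might be intended. None is named.

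**Conclusion.** The point holds as one of precision and specification on the parametric route, and as a gap on the non-parametric route. The gap rests on how Friedman's test is constructed and on no assumed figure.

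The precision gain rests on a correlation that the documents do not give. Under equal variances it is worthwhile against change-type contrasts and modest to negligible against an unadjusted follow-up contrast at low correlation. It is smaller on both comparisons if the entry rule narrows baseline. The cost of adjusting when it does not help is small. The change should be made, but the planned parametric results would not be wrong without it.

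**What to change.** 1. Replace Friedman's test for arm comparisons with a rank-based ANCOVA (Quade) on the chosen contrast. Judge normality on the model residuals.
2. Fit a linear mixed model to post-baseline VAS with arm, visit (categorical), arm × visit, baseline and baseline × visit as fixed effects, and an unstructured within-patient covariance. Use the same model for ODI and the QLQ scales, each with its own baseline.
3. Report adjusted differences for PRF v TRF, PRF v control and TRF v control with 95% confidence intervals at every visit. Either name one pair as primary, or test the 2-df arm effect on the main contrast first and the pairs only if it is significant. With three arms, that order keeps the family-wise error at 5%.
4. Reconcile the three visit lists and name the visit, or the average of visits, for the main contrast. Keep the arm × visit test, because effects may fade.

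The cost is wording only if outcome data have not been seen: no new data, and SPSS, which is already planned, fits the model. The front matter gives "Recruitment Completed: 30 July 2018" and a document date of 31 March 2019. If outcomes had been seen, this becomes a re-analysis of data already collected and must be labelled post hoc.
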